11.1 Description of efficacy variables

Assessment of Spondyloarthritis International Society criteria (ASAS) response criteria

[figure not shown]
The ASAS response measures consist of the following assessment domains ([Sieper 2009](#))

Main ASAS domains:

1. Patient's global assessment of disease activity measured on a VAS scale
2. Patient's assessment of back pain, represented by either total or nocturnal pain scores, both measured on a VAS scale. For ASAS response analyses, the total back pain will be used.
3. Function represented by BASFI average of 10 questions regarding ability to perform specific tasks as measured by VAS scale
4. Inflammation represented by mean duration and severity of morning stiffness, represented by the average of the last 2 questions on the 6-question BASDAI as measured by VAS scale (at least one question is needed)

Additional assessment domains:

5. Spinal lateral flexion, represented by one of the components of BASMI
6. C-reactive protein (acute phase reactant)

ASAS components

Patient's global assessment of disease activity (VAS)

The patient's global assessment of disease activity will be performed using a 100 mm visual analog scale (VAS) ranging from not severe to very severe, after the question "*How active was your disease on average during the last week?*".

Patient's assessment of total back pain and nocturnal back pain intensity (VAS)

The patient's assessment of back pain will be performed using a 100 mm VAS ranging from no pain to unbearable pain, after the question "*Based on your assessment, please indicate what is the amount of back pain at any time that you experienced during the last week?*" and "*Based on your assessment, please indicate what is the amount of back pain at night that you experienced during the last week?*".

Bath Ankylosing Spondylitis Functional Index (BASFI)

The BASFI is a set of 10 questions designed to determine the degree of functional limitation in those subjects with AS. The ten questions were chosen with a major input from subjects with AS. The first 8 questions consider activities related to functional anatomy. The final 2 questions assess the subjects' ability to cope with everyday life. A 100 mm VAS is used to answer the questions. The mean of the ten questions gives the BASFI score – a value between 0 and 10. In the case that some of the BASFI questions are missing, then the average of the non-missing items is used ([Braun 2009](#), [van Tubergen 2001](#)).

[figure not shown]
Bath Ankylosing Spondylitis Disease Activity Index (BASDAI)

[figure not shown]
The gold standard for measuring and evaluating disease activity in AS is the BASDAI. The BASDAI consists of a 0 through 10 scale (0 being no problem and 10 being the worst problem), which is used to answer 6 questions pertaining to the 5 major symptoms of AS:

[figure not shown]
1. Fatigue
2. Spinal pain
3. Joint pain / swelling
4. Areas of localized tenderness
5. Morning stiffness severity
6. Morning stiffness duration

To give each symptom equal weighting, the mean (average) of the two scores relating to morning stiffness is taken and is then added to the sum of the first 4 questions. The resulting 0 to 50 score is divided by 5 to give a final 0 – 10 BASDAI score. Scores of 4 or greater suggest suboptimal control of disease, and subjects with scores of 4 or greater are usually good candidates for either a change in their medical therapy or for enrollment in clinical trials evaluating new drug therapies directed at AS. BASDAI is a quick and simple index taking between 30 secs and 2 mins to complete. At least 4 questions should be non-missing to calculate the BASDAI score. Otherwise, BASDAI score will be missing ([Haywood 2002](#)). If both Q5 and Q6 are missing or one of Q1 to Q4 is missing, then the total sum should be divided by 4

instead of 5. If two of Q1 to Q4 is missing and both Q5 and Q6 are not missing, then the sum should be divided by 3.

11.2 Description of health-related quality of life variables

Ankylosing Spondylitis Quality of Life (ASQoL)

The ASQoL is a self-administered questionnaire designed to assess health-related quality of life in adult patients with Ankylosing Spondylitis. The ASQoL contains 18 items with a dichotomous yes/no response option. A single point is assigned for each "yes" response and no points for each "no" response resulting in overall scores that range from 0 (least severity) to 18 (highest severity). As such, lower score indicate better quality of life. Items include an assessment of mobility/energy, self-care and mood/emotion. The recall period is "at the moment," and the measure requires approximately 6 minutes to complete.

[figure not shown]
At least 15 answered questions are required to be able to calculate ASQoL using mean imputation, $(\text{sum of answered})/(\text{number answered}) * 18$ ([Doward 2003](#))

[figure not shown]
SF-36

The Short Form Health Survey (SF-36) is a widely used and extensively studied instrument to measure health-related quality of life among healthy subjects and patients with acute and

chronic conditions. It consists of eight subscales (domains) that can be scored individually: Physical Functioning, Role-Physical, Bodily Pain, General Health, Vitality, Social Functioning, Role- Emotional, and Mental Health. Two overall summary scores, the Physical Component Summary (PCS) and the Mental Component Summary (MCS) also can be computed. The SF-36 has proven useful in monitoring general and specific populations, comparing the relative burden of different disease, differentiating the health benefits produced by different treatments, and in screening individual patients. The eight domains are based on a scale from 0-100 while PCS and MCS are norm-based scores with a mean of 50 and a standard deviation of 10.

Quality metric uses weighted maximum likelihood estimation, a modified version of item response theory (IRT) to estimate scale scores when a respondent is missing multiple items. The PCS summary score measure requires scores for seven scales, one of which must be the PF scale and the MCS score also requires scores for seven scales, one of which must be the MH scale. Only one item is needed for each of the multi-item domains.

11.3 Handling of missing data

Missing data for ASAS20/40 response and other binary efficacy variables (e.g., ASAS5/6, etc.) for data up to Week 16 will be handled as follows:

1. Patients who drop out of the trial for any reason will be considered as non-responders from the time they drop out through Week 16.
2. Patients who do not have the required data to compute responses (e.g., ASAS components) at baseline and at the specific timepoint will be classified as non-responders at the specific timepoint.

Patients who are unblinded prior to the scheduled timepoint will be considered non-responders from the time of unblinding up to Week 16. The primary analysis will use non-responder imputation.

Continuous variables (e.g., ASAS components) will be analyzed using a mixed-effects model repeated measures (MMRM) which is valid under the missing at random (MAR) assumption. As such, single-point imputation of missing data will not be performed (e.g., LOCF). For analyses of these parameters, if all post-baseline values are missing then these missing values will not be imputed and this patient will be removed from the analysis of the corresponding variable, i.e., it might be that the number of patients providing data to an analysis is smaller than the number of patients in the FAS. Model will be based on randomized treatment (Week 1 to Week 16).

Data collected after Week 16 will generally be presented as ‘observed case’; i.e. all available data for each time point will be included in the analyses.

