9.4.3 Handling of missing values/censoring/discontinuations

Missing data for ASAS20/40 response and other binary efficacy variables (e.g. ASAS5/6, etc.) will be handled as follows:

1. Subjects who drop out of the trial for any reason will be considered non-responders from the time they drop out through week 16
2. Subjects who do not have the required data to compute response (e.g. ASAS components) at baseline and at the specific time will be classified as non-responders.

Patients who were unblinded prior to the scheduled time point will be considered non-responders from the time of unblinding up to Week 16. The primary analysis will use the non-responder imputation.

Continuous variables (e.g. ASAS components) will be analyzed using a mixed-effects model repeated measures (MMRM) which is valid under the missing at random assumption. For analyses of these parameters, if all post-baseline values are missing then these missing values will not be imputed and this subject will be removed from the analysis of the corresponding

variable, i.e. it might be that the number of subjects providing data to an analysis is smaller than the number of subjects in the FAS.

Data collected after Week 16 will be analyzed as observed cases, in general.

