11.5 Analysis of secondary variables

The secondary efficacy variables include,

- response to treatment at Week 16 according to the ASAS40 criteria
- change from baseline in hsCRP at Week 16
- response to treatment at Week 16 according to the ASAS5/6 criteria
- change from baseline in total BASDAI score at Week 16
- change in SF-36 PCS from baseline at Week 16
- change in ASQoL from baseline at Week 16
- response to treatment at Week 16 according to the ASAS partial remission

All analysis will be done in the FAS population.

Testing strategy to control type I error

The following null hypotheses will be included in the testing strategy, and type-I-error will be set such that a family-wise type-I-error of 5% is kept:

Primary objectives:

H₁: secukinumab 150 mg regimen is not different to placebo regimen with respect to signs and symptoms (ASAS20 response) at Week 16

Secondary objectives:

H₂: secukinumab 150 mg regimen is not different to placebo regimen with respect to signs and symptoms (ASAS40 response) at Week 16

H₃: secukinumab 150 mg regimen is not different to placebo regimen with respect to change from baseline in hsCRP at Week 16

H₄: secukinumab 150 mg regimen is not different to placebo regimen with respect to ASAS 5/6 response at Week 16

[figure not shown]
H₅: secukinumab 150 mg regimen is not different to placebo regimen with respect to change from baseline in total BASDAI at Week 16

H₆: secukinumab 150 mg regimen is not different to placebo regimen with respect to change from baseline in SF-36 PCS at Week 16

H₇: secukinumab 150 mg regimen is not different to placebo regimen with respect to change from baseline in ASQoL at Week 16

H₈: secukinumab 150 mg regimen is not different to placebo regimen with respect to ASAS partial remission criteria at Week 16

Figure 11-1 Testing strategy

The family-wise error will be set to $\alpha=5\%$ and it will be controlled with the proposed closed testing procedure.

The secondary efficacy variables and the method for adjusting for multiplicity are described below. Secondary efficacy variables will be analyzed using the FAS population.

ASAS40 at Week 16

The ASAS 40 response is defined as an improvement of $\geq 40\%$ and ≥ 2 units on a scale of 10 in at least three of the four main domains and no worsening at all in the remaining domain.

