11.7 Analysis of health-related quality of life variables

Ankylosing Spondylitis Quality of Life (ASQoL)

For the change in ASQoL scores, between-treatment differences in the change in ASQoL scores will be evaluated using a mixed effect repeated measures model (MMRM). Treatment group, analysis visit, randomization stratum (region) will be used as categorical factors and baseline ASQoL score and baseline weight as continuous covariates. Treatment by analysis visit and baseline ASQoL score by analysis visit will be included as interaction terms in the model. An unstructured covariance structure will be assumed for the model. The significance of the secukinumab treatment effect at different analysis visits will be determined from comparison performed between secukinumab regimen and placebo at the appropriate analysis visits.

The proportion of subjects with improvements from baseline in ASQoL score meeting or exceeding minimal clinically important difference (MCID) will also be analyzed using a logistic regression model with treatment and randomization stratum (region) as factors, baseline ASQoL score and baseline weight as covariates up to Week 16. Odds ratios and 95% CI will be presented for treatment comparison. Post Week 16 the proportion of responders will be descriptively summarized along with its 95% confidence intervals for each treatment sequence.

SF-36

The following variables will be evaluated:

[figure not shown]
- SF-36 domain scores (based on a scale of 0-100).
- SF-36 PCS and MCS scores (norm-based scores).
- SF-36 PCS responder (improvement of ≥ 2.5 points, [Lubeck 2004](#))

For the change in SF-36 summary scores (PCS and MCS), between-treatment differences will be evaluated using a mixed effect repeated measures model (MMRM). Treatment group, analysis visit and randomization stratum (region) will be included as categorical factors and baseline SF-36 score (PCS or MCS) and baseline weight as continuous covariates. Treatment by analysis visit and baseline SF-36 score (PCS or MCS) by analysis visit will be included as interaction terms in the model. An unstructured covariance structure will be assumed for the model. The significance of the secukinumab treatment effect at different analysis visits will be determined from comparison performed between secukinumab regimen and placebo at the appropriate analysis visits.

[figure not shown]

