In the responder analyses, treatment groups will be compared with respect to response to treatment using a logistic regression model with treatment and randomization stratum (region)

[figure not shown]
as factors, baseline SF-36 PCS score and baseline weight as covariates up to Week 16. Odds ratios and 95% CI will be presented for treatment comparison. Post Week 16, the proportion of responders will be descriptively summarized along with its 95% confidence intervals for each treatment sequence.

The SF-36 domain scores will be summarized.

12 [REDACTED] evaluations (change / add PD, [REDACTED]/PD,
Biomarkers, as needed)

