15.1 Power for analysis of secondary variables

A summary of the assumptions and power for the primary and secondary efficacy parameters using the same unpublished study is shown in [Table 15-1](#) for binary endpoints and [Table 15-2](#) for continuous endpoints.

Table 15-1 Summary of power for binary endpoints

Endpoint	Response Rate		Power
	Secukinumab 150 mg (N=300)	Placebo (N=150)	
ASAS20	61.1%	28.4%	99%
ASAS40	36.1%	10.8%	99%
ASAS5/6	43.1%	8.1%	99%
ASAS partial remission	13.9%	4.1%	92%

Table 15-2 Summary of power for continuous endpoints

Endpoint	Mean change from baseline		Common standard deviation	Power
	Secukinumab 150 mg (N=300)	Placebo (N=150)		
hsCRP	-0.60	0.12	0.84	99%
Total BASDAI	-2.19	-0.85	2.10	99%

Endpoint	Mean change from baseline		Common standard deviation	Power
	Secukinumab 150 mg (N=300)	Placebo (N=150)		
SF-36 PCS	6.06	1.92	6.65	99%
ASQoL	-4.00	-1.37	4.45	99%

16 Appendix

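### Does the move from non-responder imputation to observed case at Week 16 distort the ASQoL and SF-36 PCS responder rates?

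*SAP*

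**What the plan says.** SAP 11.3 opens its rule with "Missing data for ASAS20/40 response and other binary efficacy variables", gives ASAS 5/6 as a further example, and limits the rule to data up to Week 16. Patients who leave the trial "will be considered as non-responders from the time they drop out through Week 16". Patients lacking the data needed to compute a response are non-responders at that visit, and unblinded patients are non-responders from unblinding to Week 16. Later data are generally presented as observed case, meaning that "all available data for each time point will be included in the analyses". Protocol 9.4.3 draws the same line: "Data collected after Week 16 will be analyzed as observed cases, in general".

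SAP 11.7 defines two responder variables: ASQoL improvement reaching the minimal clinically important difference, and SF-36 PCS improvement of at least 2.5 points. Each is compared between arms by logistic regression up to Week 16. For ASQoL the text then continues: "Post Week 16 the proportion of responders will be descriptively summarized along with its 95% confidence intervals for each treatment sequence". The SF-36 PCS text says the same. Section 11.7 gives no missing-data rule of its own in the text available.

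In SAP 11.5 the tested secondary variables are the change scores, for example "change in SF-36 PCS from baseline at Week 16", analysed by MMRM. The two responder variables are not among H1 to H8.

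**The concern.** The same responder rate appears to be reported under two rules. Through Week 16 a patient without data stays in the denominator as a failure; afterwards that patient drops out of it. With no change in anyone's response, the reported percentage would rise once Week 16 is passed.

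Protocol 1.2 says the study is to provide up to 52 weeks of efficacy, safety and tolerability data to support registration, so someone may well read these rates as a time course. Protocol 5.5.9.1 makes lack of improvement a reason to stop treatment. If patients without data respond less often than those with data, observed-case rates would also be too high in absolute terms. The missing-data sensitivity analyses in SAP 11.4 concern ASAS20 only, and no planned table is described as showing Week 16 under both rules.

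**Working it through.** The point rests on no sample size, power or alpha figure, so the plan has no figure to reproduce. The check has three parts: the size of the step, what the step means, and whether it can be seen from the planned output.

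**Inputs**
- SF-36 PCS change, secukinumab: mean 6.06, SD 6.65. ASQoL change, secukinumab: mean -4.00, SD 4.45. SF-36 PCS change, placebo: mean 1.92. All are from SAP Table 15-2 ("Summary of power for continuous endpoints").
- SF-36 PCS responder threshold: 2.5 points (SAP 11.7).
- Planned dropout at the primary endpoint: 10% (Protocol 4).
- Arm sizes: 300 and 150.
- Assumptions: changes are normal; the table values describe patients with data; dropout equals the missing share. The ASQoL threshold is not in the available text, so 1 to 4 points is used as a range.

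**1. Size of the step.** Let r be the response rate among patients with data and d the missing share. Observed case reports r, non-responder imputation reports r(1 - d), and the step is d × r.

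- PCS, secukinumab: r = Φ((6.06 - 2.5)/6.65) = Φ(0.535) = 0.704.
- d = 0.10: 0.704 × 270 = 190 responders. 190/270 = 70.4% and 190/300 = 63.3%; step = 0.10 × 0.704 = 7.0 points.
- d = 0.05: 0.704 × 285 = 201 responders. 201/300 = 67.0%; step = 3.5 points.
- PCS, placebo: r = Φ((1.92 - 2.5)/6.65) = 0.465; step at d = 0.10 is 4.7 points.
- ASQoL, secukinumab: r = Φ((4.00 - t)/4.45) = 0.750, 0.673, 0.589, 0.500 for t = 1, 2, 3, 4; steps at d = 0.10 are 7.5, 6.7, 5.9, 5.0 points.

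**2. What the step means.** It is the gap between two rules, not the bias of either. The bias of observed case is d × (r_obs - r_miss). For PCS at d = 0.10:

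| Response among patients without data | Bias of observed case (points) |
|---|---|
| none | +7.0 |
| half as often (0.352) | +3.5 |
| equally often (0.704) | 0 |
| 1.2 times as often (0.845) | -1.4 |

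As a time course, suppose 70.4% of patients with data respond at both visits, 10% lack data at Week 16 and an assumed 10 to 20% at Week 52. The mixed rules show 63.3% then 70.4% (+7.0). Observed case throughout shows no change. Non-responder imputation throughout shows 63.3% then 63.3% to 56.3% (0 to -7.0). The documents give no dropout rate after Week 16, so the real figure cannot be computed.

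The visit windows soften the effect. For SF-36 and ASQoL, SAP Table 16-1 sets Week 16 at Days 72 to 141 and Week 52 at Days 268 to 379. An end-of-treatment visit 28 days after a Week 8 dose falls on Day 57 + 28 = 85, inside the Week 16 window. After a Week 36 dose it falls on Day 253 + 28 = 281, inside the Week 52 window. Some early stoppers will therefore have data at those visits, although one who has left the trial before Week 16 still counts as a non-responder there.

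**3. Can a reader see it?** SAP 16.2.1.1 provides N by visit and treatment group for continuous data, which includes the PCS and ASQoL scores. SAP 16.2.2.1 provides counts and frequencies for discrete variables. Imputed non-responders add nothing to the responder count, so:
- Week 16 observed-case rate = Week 16 responders / N with a score (190/270 in the example);
- later non-responder rate = later responders / number in that treatment sequence in the FAS.

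The first is exact except for a patient who has a score but is set to non-responder because of unblinding or dropout.

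**The case for a change.** The best case for acting is that a registration dossier may show these rates by visit, that a flat response could look like a 7-point gain, and that the remedy is a few descriptive tables using a multiple-imputation template the SAP already contains (16.2.3.1). It is also fair that SAP 11.3 does not say whether its rule reaches the quality-of-life responders. SAP 11.5 counts the SF-36 PCS and ASQoL changes as efficacy variables, which favours coverage, but the named binary examples are all ASAS measures.

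The arithmetic and the silence on scope both stand. The rest carries less weight. If the rule does not cover these two variables and they are observed case throughout, there is no step at all. If it does, the split is openly stated in both documents. SAP section 3 confines comparative efficacy to the first 16 weeks and makes later summaries descriptive by treatment sequence. The objectives in Protocol 2.1 and the efficacy objectives in 2.2 are all set at Week 16, so none relies on a trend from Week 16 to Week 52.

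A single rule would not make the two periods comparable either. Treatment is open-label from Week 16, the placebo group starts secukinumab then, and escape medication and analgesic changes are allowed after Week 20. Non-responder imputation carried through a year has its own downward pull. Because SAP section 3 calls for tables for the Chinese and the overall population separately, each added table would be produced twice.

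**Conclusion.** No change to the plan is needed. The change of basis is real if the non-responder rule covers these responders, and it could move the secukinumab PCS rate by about 3.5 to 7 points at 5 to 10% missing. That size rests on assumed normality, on an earlier study's mean and SD, and on treating planned dropout as missing questionnaires. It affects only descriptive rates for two variables outside the testing hierarchy. The primary endpoint, the tested secondary endpoints, type I error and power are untouched.

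Observed case for an open-label period is a fair, prespecified choice, and the planned N and counts let a reader closely rebuild the other basis. Whether the rule covers these two variables, and which denominator applies at each visit, are details an analyst would settle in the table shells and footnotes. A parallel imputed series would add output without altering any conclusion the trial is meant to support.

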11.4 Analysis of primary variable

The primary efficacy variable is response to treatment according to the ASAS20 criteria at Week 16. The analysis of the primary variable will be based on the FAS patients.

Description

The ASAS Response Criteria (ASAS20) is defined as an improvement of $\geq 20\%$ and ≥ 1 unit on a scale of 10 in at least three of the four main domains and no worsening of $\geq 20\%$ and ≥ 1 unit on a scale of 10 in the remaining domain.

Statistical analyses

The statistical hypothesis for ASAS20 being tested is that there is no difference in the proportion of subjects fulfilling the ASAS20 criteria at Week 16 in secukinumab regimen versus placebo regimen.

Let p_0 denote the proportion of ASAS20 responders at Week 16 for Placebo regimen and p_1 denote the proportion of ASAS20 responders at Week 16 for Secukinumab 150 mg regimen,

In statistical terms, $H_0: p_1 = p_0$, $H_{A1}: p_1 \neq p_0$, i.e.

H_1 : Secukinumab 150 mg regimen is not different to placebo regimen with respect to ASAS20 response at Week 16

The primary analysis will be conducted via logistic regression with treatment, randomization stratum (region) as factors and baseline weight as a covariate. Odds ratios and 95% CI will be presented comparing secukinumab 150 mg regimen to placebo.

Supportive analyses

Sensitivity analyses and supportive analyses will be conducted in order to provide evidence that the results seen from the primary analysis are robust.

In order to determine the robustness of the logistic regression model used for the primary analysis, ASAS20 response at Week 16 will also be evaluated using a non-parametric

ANCOVA model ([Koch 1998](#)) with the same independent variables as the logistic regression model.

Interactions between treatment and selected baseline demographics and disease characteristics will be explored.

The impact of missing data on the analysis results of ASAS20 response will be assessed as well by repeating the logistic regression model using different ways to handle missing data. These may include, but are not limited to:

- Multiple imputation
- Observed data analysis

